| 
Objectives:
 
The Primary Objective of the study is to evaluate the implantation rate increase in women undergoing Assisted Reproductive Technique (ART) by using Forielle, an endometrial wash that restores favourable conditions of endometrial “milieu” after Controlled Ovarian Stimulation (COS).
 
Secondary objectives are to:
 
 • Determine the Pregnancy Rate at PET Day 14 • Determine the Ongoing Pregnancy Rate during PET Days 70 to 84 • Assess the safety of Forielle by report of device incidents | |

Substance Code Clinical Performance and Safety Investigation of ENDOmetrial Washing
MEdical DEvice Forielle
Protocol Number MS 700623_0009

Methodology:

This is a multicentre, prospective randomised controlled, interventional investigation to assess the safety and clinical performance of Forielle, a medical device for endometrial washing, in restoring favourable endometrial condition to implantation after COS during ART. The study protocol consists of assessing the clinical performance of Forielle in restoring favourable condition of endometrial milieu after COS. Clinical performance will be measured by comparing implantation rate in the treated arm compared to the control. The trial aims to enrol 2,156 women from at least six centres in Italy.

Infertile females aged ≤ 41 years with no more than one previous implantation failure will be assessed for eligibility for the trial after providing written informed consent. Subjects will undergo COS according to standard of care clinical practice. There is no limitation in the gonadotrophin stimulation protocols used; however, triggering must be done with HCG. Eligible subjects will be randomised to receive either the intervention (Forielle endometrial washing) or no endometrial washing following oocyte retrieval on Study Day 0, the HCG Triggering day, in a 1:1 ratio. Oocyte retrieval and endometrial washing (Forielle-treated group) will occur during the same surgical procedure. The entire ART cycle will be performed according to clinical practice of the centre based on each subject's clinical profile.

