As appropriate, variables will be summarized descriptively (frequency and percentage will be summarized for categorical variables; mean, standard deviation [SD], median, and maximum will be presented for continuous variables) by study visit and by treatment group. All study data will be listed by subject. A detailed Statistical Analysis Plan (SAP) including dictionaries used for coding and software used will be prepared separately for interim and final analysis. Study final analysis will be performed by PPD and Interim analysis will be performed by a PPD independent statistician from a different geographical region. A firewall will be implemented to ensure interim results will not be accessible to any PPD staff except to the independent statistician who will perform interim analysis.

Forielle Clinical Performance

The primary endpoint, subject implantation rate, is defined as number of intrauterine gestational sacs divided by the number of embryos transferred, as assessed at PET Days 21 to 28. Mean subject implantation rate, as assessed at PET Days 21 to 28 in subjects treated with Forielle endometrial washing procedure, will be compared to the mean subject implantation rate in subjects who receive no endometrial washing (control group) following COS.

For the primary endpoint analysis addition to summary statistics, differences in mean subject implantation rate between study procedure and control procedure will be investigated and compared using Gamma/log normal regression model. The analysis model will include treatment procedure as the fixed effect and Embryo Transfer Day (Day 5 PR or Day 7 PR), age, number of follicles at baseline and number of embryos transferred per subject as covariates.

To evaluate the treatment comparison, estimated mean differences will be presented together with two-sided 95% confidence intervals and p-values. Appropriate distribution will be decided based on good ness of fit (residual sum of squares) value. This primary clinical performance endpoint analysis will be tested by planned group sequential design with O'Brien-Fleming type spending function. The study for clinical performance will be stopped at significance level of 0.003 in first (50% of subjects) interim analysis and at significance level 0.049 in final analysis.

Safety

Device incidents will be summarized using frequency and percentages for two treatment groups.

Table 1-1 Schedule of Assessments

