Major lines of evidence confirmed that ovarian stimulation reduces endometrial receptivity, even if, recently, some authors reported that this happens only in high responders, while in low and average responders it does not (Yeh 2014). Starting from genes expression (Blockeel 2011; Mariee 2012; Haouzi 2014) to histology (Evans 2012; Li 2013), from immunologic mechanisms (Evans 2012) to vascularity (Kim 2014), transcriptomics (Haouzi 2009; Detti 2011; Blesa 2014; Díaz-Gimeno 2014), proteomic (Garrido-Gómez 2014) and secretomic (Hannan 2010; Cheong 2013; Galliano 2014), all these aspects of endometrium biology may affect its receptivity in ART cycles. As a result, Garcia-Flores et al. (Garcia-Flores 2013) found that some patients have a delayed window of implantation, others have an advanced one, and others show unusually short windows of receptivity. This problem has been hypothesized to be related with a particular pattern of progesterone and estrogen receptors expression, found in oocyte donors during an ART cycle (Detti 2011) and other authors, more recently, confirmed these evidences (Tapia-Pizarro 2014). Thin endometrium is a problem often related to implantation failure and its assessment and management have been proposed as approaches aimed at improving pregnancy rates (Lebovitz 2014) in ART, even if some authors published data that contradicted this argument (Gingold 2014). Revel et al. and Evans et al. suggested a role for MicroRNAs as diagnostic markers and therapeutic tools for implantation disorders in ART (Revel 2011; Evans 2012), while a well-established line of research studied profiles of genes expression related to endometrium receptivity. In particular, HOXA-10, leukemia inhibitory factor, and cleavage stimulation factor genes expression has been showed to correlate with endometrium receptivity and with clinical pregnancy as well (Garcia-Flores 2013). Moreover, Sak et al., comparing fibroblast growth factor-1 (FGF-1) gene expression in patients who underwent in vitro fertilization (IVF) and had repeated implantation failure, with fertile patients, found that the expression of this gene was reduced in patients and concluded that growth factors, such as FGF-1, could be relevant in promoting implantation (Sak 2013). Other authors found that IL-15 expression is related to higher risk of implantation failure (Mariee 2012). On the other hand, Boomsma et al., in 2009, already showed that changes in cytokines profile expression in endometrial aspirates was so characteristic in stimulated cycles, that assessment of these modifications were proposed as a marker of endometrial receptivity (Boomsma 2009). Aflatoonian et al. in 2014 reviewed the negative effects of some of these proteins and cytokines on implantation (Aflatoonian 2014). Changes in genes expression induced by ovarian stimulation protocols depend even on the protocols used. In fact, some authors found that with GnRH antagonist the profile of genes expression related to endometrial receptivity is more similar to the one of natural cycles, compared with GnRH agonist protocols (Haouzi 2010). These findings contradicted previous studies that emphasized the negative effects of GnRH antagonists on endometrium receptivity (Rackow 2008).

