7.1.2.2 Stimulation Control (Day -8)

Potential subjects will return to the study site approximately 2 days after the start of stimulation (Day -8) for a COS Control Visit. At the COS control visit, the following assessments and procedures will occur:

- Follicular assessment, to include follicle counts, measure of the follicles overall size (two diameters of circumference required)
- Endometrial assessment, to include measurement of endometrial thickness
- Record adverse events and concomitant medications

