8.1 Sample Size

The main aim of the study is the evaluation of the clinical performance of Forielle in restoring favourable condition of endometrial milieu, after Controlled Ovarian Stimulation. For this purpose, clinical performance will be measured by assessing the difference in implantation rate in the treated arm compared to the control (standard clinical practice). Generally, the average implantation rate of ART is considered of about 25% (Nastri et al. 2013). Several works in the literature suggested the key role of endometrial receptivity on the ART outcomes (Evans et al. 2012). An improvement of about 6% in implantation rate from the usual ART outcome is clinically relevant difference. Thus, for the calculation of sample size, a clinically important difference of 6% was assumed and an interim clinical performance analysis assuming that 2 sequential tests are made using the O'Brien-Fleming spending function to determine the test boundaries. Sample sizes of 916 each arm achieve 80% power to detect a difference of 0,06 between the group proportions of 0,25 and 0,31 at a significance level (alpha) of 0,050 using a two-sided z-test with continuity correction and allocation ratio of 1:1. The total number of women to be randomised is 2,156, considering a drop-out rate of 15%.

| Target Power | Actual Power | N1 | N2 | N | P1 | P2 | Alpha |
|--------------|--------------|-----|-----|------|------|------|-------|
| 0.80 | 0.80025 | 916 | 916 | 1832 | 0.25 | 0.31 | 0.05 |

Substance Code Clinical Performance and Safety Investigation of **ENDO**metrial Washing
MEdical **DE**vice Forielle
Protocol Number MS 700623_0009

Details when Spending = O'Brien-Fleming, N1=916, N2=916, P1=0,25, P2=0,31, Continuity Correction.

| Look | Time | Lower Boundary | Upper Boundary | Nominal Alpha | Incremental Alpha | Total Alpha | Incremental Power | Total Power |
|------|------|----------------|----------------|---------------|-------------------|-------------|-------------------|-------------|
| 1 | 0.5 | -2.96259 | 2.96259 | 0.003 | 0.003 | 0.003 | 0.16425 | 0.164 |
| 2 | 1 | -1.96857 | 1.96857 | 0.049 | 0.047 | 0.047 | 0.63600 | 0.800 |

The required significance level for stopping the study for clinical performance is 0.003 to first look (50% of patients) and 0.049 at second look (final). The overall power is 80%.

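### Endometrial thickness is measured before randomisation and linked by the background to implantation failure, but the primary model does not use it; adding it would be a small, cheap gain in precision.

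*Combined protocol and SAP*

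**What the plan says.** **Background (section 3).** On thickness: "Thin endometrium is a problem often related to implantation failure". That sentence goes on to acknowledge published data to the contrary. On stimulation: "Changes in genes expression induced by ovarian stimulation protocols depend even on the protocols used". The text that follows compares GnRH agonist and antagonist cycles and says the newer findings conflict with older ones.

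**Collection.** Sections 7.1.2.1 (Day -12 to -10) and 7.1.2.2 (Day -8) each list this item: "Endometrial assessment, to include measurement of endometrial thickness". Both visits precede randomisation on Day 0. Section 7.1.2.3 (Day 0) names the follicle count and hormone levels but not thickness. Table 1-1 has a row for follicular and endometrial assessment during stimulation.

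**Stimulation protocol.** Sections 1 and 5.1: "There is no limitation in the gonadotrophin stimulation protocols used".

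**Analysis.** The primary model (section 1 and 8.5.2) has treatment and transfer day, with "age, number of follicles at baseline and number of embryos transferred per subject as covariates". The logistic models in 8.5.3 have transfer day, age and follicle number. Randomisation is stratified by age and follicles above 16 mm (6.3, 8.2). Thickness appears in none of these.

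**The concern.** The device is meant to act on the endometrium, and section 5.2 chooses implantation rate as an endpoint that reflects endometrial receptivity. Thickness is the one quantitative endometrial measurement that the visit text requires before the wash. If it predicts implantation, leaving it out keeps explainable variation in the error term and leaves any chance difference between arms in baseline thickness in the estimate. Adjusting for a value fixed before randomisation is safe, provided it is specified in advance. What is at stake is therefore precision, not validity.

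**Working it through.** **Inputs.** Section 8.1 gives "Sample sizes of 916 each arm achieve 80% power to detect a difference of 0,06", "between the group proportions of 0,25 and 0,31", and "at a significance level (alpha) of 0,050 using a two-sided z-test with continuity correction and allocation ratio of 1:1". It also gives two looks at 50% and 100% information with bounds 2.96259 and 1.96857, and 15% drop-out. The documents give no R-squared or odds ratio for thickness, so these are assumed below.

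**Step 1: reproduce the plan.** The mean rate is (0.25 + 0.31)/2 = 0.28.
- Expected Z at the final look: (0.06 - 1/916) / sqrt(2 × 0.28 × 0.72 / 916) = 0.05891 / 0.02098 = 2.81.
- Expected Z at the interim, 458 per arm with its own continuity correction: (0.06 - 1/458) / sqrt(2 × 0.28 × 0.72 / 458) = 1.95.
- Bivariate normal integration with correlation sqrt(0.5) and the stated bounds gives overall alpha 0.0500 and power 0.8002. The smallest n reaching 80% is 916 per arm.
- Using 1/916 as the correction at both looks gives first-look power 0.164 and total power 0.8003, against the plan's 0.164 and 0.80025.
- 916/0.85 = 1,077.6, so 1,078 per arm and 2,156 in total.

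The plan's figures reproduce.

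**Step 2: add the covariate.** Multiply the outcome variance by (1 - R²), where R² is what thickness explains beyond the covariates already in the model. The expected Z is divided by sqrt(1 - R²). At R² = 0.02 the final value is 2.8078 / sqrt(0.98) = 2.836.

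| Assumed added R² | Power at 916 per arm | n per arm for 80% |
|---|---|---|
| 0% | 80.0% | 916 |
| 0.5% | 80.2% | 912 |
| 1% | 80.4% | 907 |
| 2% | 80.8% | 898 |
| 3% | 81.2% | 890 |
| 5% | 82.0% | 872 |

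**Step 3: put the assumed R² on a familiar scale.** Take thickness as a standard normal covariate in a logistic model with mean rate 0.28, and R² = Var(p) / (0.28 × 0.72). Odds ratios of 1.1, 1.2, 1.3 and 1.5 per SD give R² of 0.2%, 0.7%, 1.4% and 3.2%. An added R² above 2% would thus need an odds ratio somewhere between 1.3 and 1.5 per SD.

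**Step 4: chance imbalance.** At the 95% limit the arms differ by 1.96 × sqrt(2/916) = 0.092 SD in thickness. The shift in the unadjusted difference is about 0.092 × ln(OR) × 0.28 × 0.72, which is 0.2, 0.3, 0.5 and 0.7 percentage points for the four odds ratios. The standard error of the difference is sqrt((0.25 × 0.75 + 0.31 × 0.69)/916) = 2.1 points, and the target is 6 points.

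**Step 5: Day 0.** In the text copy of Table 1-1 the columns do not line up reliably. The row for follicular and endometrial assessment is marked in its second and third cells. The HCG injection, which happens only on Day 0, is marked in that same third cell. So the table probably includes an endometrial assessment on Day 0, whereas 7.1.2.3 does not mention one. This is an inference that the sponsor can settle from the original table.

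**The case against.** The strongest reply is that thickness may not predict implantation at all. The background cites contrary data, and the title of the contrary source in section 11 reports no effect of thickness on implantation rates in euploid transfers. The Day -8 reading falls only about 2 days into stimulation, and nothing in the documents shows how informative it is then. Chance imbalance is already covered by the test's error rate and the confidence interval. All of this stands. It makes the gain uncertain and possibly nil. It does not make pre-specified adjustment harmful, since the cost is one parameter among about 1,832 women.

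A reader might infer several stronger points, which the documents do not support:
- *That stimulation protocol type should also enter the primary model.* Section 3 ties it to gene expression and receptivity, with conflicting findings, and not to implantation rate. No CRF item for it is named, and 6.5 keeps standard ART procedures out of the concomitant therapy record. Section 10.3 keeps hormones administered as source documents only.
- *That thickness is collected and never reported.* The synopsis provides for summaries by visit and treatment group, as appropriate, and for listings of all data.
- *That the last reading is certainly Day -8.* Table 1-1 suggests otherwise.
- *That the secondary models must change too.* Section 8.5.1 makes secondary comparisons descriptive, so the power argument does not reach them, and adding a covariate to a logistic model changes the conditional odds ratio being estimated.

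Section 8.5.1 also defers detail to separate SAPs. Section 8.5.2 nevertheless already lists the covariates, so an addition belongs there.

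**Conclusion.** The point holds as a minor, optional improvement. A baseline value that the background itself connects, with acknowledged doubt, to the outcome is collected and left out of the primary model. Adding it is worth between nothing and about one power point: 80.0% to 80.8% for an added R² of 0% to 2%, and 81.2% at 3%. The R² range is an assumption, and the calculation uses a linear approximation in place of the planned Gamma/log-normal model. Randomisation protects against systematic bias with or without the covariate, and the sample size claims no covariate gain, so neither the test nor the 2,156 is affected.

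**What to change.** - **8.5.2, the synopsis and both SAPs:** add the last endometrial thickness recorded before randomisation, as a continuous covariate, to the primary model. Do this before the interim analysis, with the same covariate list at both looks.
- **7.1.2.3 and Table 1-1:** reconcile them on whether thickness is read on Day 0. If it is, state that the reading precedes randomisation and is the covariate value; if not, the Day -8 value serves. Without this, the last value could come from different days at different sites.
- **Missing values:** state a rule that does not depend on arm, for example the previous pre-randomisation reading or, failing that, the mean over both arms.
- **Stimulation protocol type:** at most an optional covariate in a sensitivity analysis, and only if a data item is created for it.
- **8.5.3:** no change.

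The cost is plan wording, one model parameter and the missing-value rule. If Day 0 thickness is to be used and has no eCRF field, one field is needed as well.

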3.1 Benefit-Risk Assessment

The analysis of the risks and benefits of Forielle demonstrated that Forielle met its safety and clinical performance requirements and the device fulfilled its intended use as claimed by Ares

Substance Code Clinical Performance and Safety Investigation of ENDOmetrial Washing
MEdical DEvice Forielle
Protocol Number MS 700623_0009

Trading S.A.. Following is a description of potential (expected) risks and benefits that may be associated with the use of Forielle. Forielle received the CE marking as a class IIa medical device.

3.1.1 Risks Related to Forielle

The Risk Analyses (Product Risk Analysis, Human Factor Risk Analysis and Clinical Risk Analysis) conducted during the whole product lifecycle process to establish the safety and the clinical performance of Forielle have not evidenced and not identified any Human factor and Clinical risks, the residual Product Risk was determined acceptable based on risk benefit analyses Product risk, identified as medium or low level, is related to device sterility that could be impacted during Medical Device Production. The related contingency plan was set as per Good Manufacturing Practice (GMP) for Sterile Product.

3.1.2 Benefits of Forielle

No market feedback data currently support directly and objectively the clinical performance benefit of Forielle, due to fact that this device has to be introduced into the market for the first time in the field of Fertility therapeutic area. Indirect evidence, from equivalent solution and equivalent methodology, suggests that Forielle might benefit patients and medical professionals by improving the environmental conditions and facilitating interventions for the preparation of the ART. This study is being conducted in order to determine the extent of beneficial effects and to confirm the clinical safety of Forielle use in standard clinical practice.

4 Trial Objectives

4.1 Primary Objective

The primary objective of this study is to evaluate the implantation rate increase in women undergoing Assisted Reproductive Technique (ART) by using Forielle, an endometrial wash that restores favourable conditions of endometrial "milieu" after Controlled Ovarian Stimulation (COS).

4.2 Secondary Objectives

The secondary objectives of the study are to:

- Determine the Pregnancy Rate at PET Day 14
- Determine the Ongoing Pregnancy Rate during PET Days 70 to 84
- Assess the safety of Forielle by report of device incidents

Substance Code Clinical Performance and Safety Investigation of ENDOmetrial Washing
MEdical DEvice Forielle
Protocol Number MS 700623_0009

5 Investigational Plan

5.1 Overall Trial Design and Plan

This is a multicentre, prospective randomised controlled, interventional investigation to assess the safety and clinical performance of Forielle, a medical device for endometrial washing, in restoring favourable endometrial condition to implantation after COS during ART.

The study protocol consists in assessing the clinical performance of Forielle in restoring favourable condition of endometrial milieu after COS. Clinical Performance will be measured by comparing implantation rate in the treated arm compared to the control. The trial aims to enrol 2,156 women from at least six centres in Italy.

Infertile females aged ≤ 41 years with no more than one previous implantation failure will be assessed for eligibility for the trial after providing written informed consent. Subjects will under COS according to standard of care clinical practice. There is no limitation in the gonadotrophin stimulation protocols used; however, triggering must be done with HCG. Eligible subjects will be randomised to receive either the intervention (Forielle endometrial washing) or no endometrial washing following oocyte retrieval on Study Day 0, the HCG Triggering day, in a 1:1 ratio. Oocyte retrieval and endometrial washing (Forielle-treated group) will occur during the same surgical procedure. The entire ART cycle will be performed according to clinical practice of the centre based on each subject's clinical profile.

Retrieved oocytes will be fertilized per ICSI standard clinic practice and the embryology lab will calculate the fertilization rate for each subject. Beginning approximately 24 hours after ICSI, the embryology lab will evaluate embryo for quality daily, with the most viable embryos selected for implantation (Day 5 PR for embryos transferred in the cleavage stage and Day 7 PR for embryos transferred in the blastocyst stage).

Luteal support/endometrial preparation will be done with progesterone (100 mg intramuscular injection at the Oocyte Pick Up [OPU] day and 600 mg of vaginal progesterone from the day after OPU and administered daily). At the Embryo Transfer visit (Day 5 PR or Day 7 PR), a maximum of 2 fertilized embryos or blastocysts will be transferred; luteal support (daily administration of 600 mg of vaginal progesterone) will continue.

All subjects must have a serum β -HCG pregnancy test performed 14 days after embryo transfer (PET Day 14). Subjects may have this assessment performed by another physician; however, the pregnancy test report must be provided to the investigator. In these cases, all other PET Day 14 assessments may be performed with the subject via telephone.

If the PET Day 14 serum β -HCG pregnancy test is negative, the PET Days 21-28 and PET Days 70-84/Weeks 10-12 visits may occur by telephone with the PET Days 70-84/Weeks 10-12 visit serving as the final study contact. In these cases, the PET Days 21-28 visit and PET Days 70-84 visits may be performed via telephone and the investigator will enter negative ultrasound results for ultrasound assessments that would have been performed at PET Days 21-28 and PET Days 70-84.

Substance Code Clinical Performance and Safety Investigation of ENDOmetrial Washing
MEdical DEvice Forielle
Protocol Number MS 700623_0009

If the PET Day 14 serum β -HCG pregnancy test is positive, the subject must return to the site 21 to 28 days after embryo transfer (PET Days 21-28), to determine the number of gestational sacs present and calculate the implantation rate, the primary endpoint. The primary endpoint, the subject implantation rate, is defined as the number of intrauterine gestational sacs divided by the number of embryos transferred.

If the subject returns to the site on PET Days 21-28 for transvaginal ultrasound and does not have any gestational sacs present, the investigator will enter a negative result for the PET Days 70-84/Weeks 10-12 obstetric ultrasound (transvaginal or abdominal). In these cases, the PET Days 70-84/Weeks 10-12 final study visit may occur by telephone.

Subjects who return to the site at PET Days 21-28 and have gestational sacs present on transvaginal ultrasound will have a final obstetric ultrasound (transvaginal or abdominal) on PET Days 70-84/Weeks 10-12 to verify the Ongoing Pregnancy Rate (OPR). In the event a subject cannot return to the site for the PET Days 70-84/Weeks 10-12 visit, ultrasound report confirming ongoing pregnancy details required (number of foetuses, confirmation of foetal vitality based on the presence of foetal heartbeat and confirmation of the development of normal pregnancy for each foetus present on ultrasound) may be provided to the investigator. In these cases, final study procedures may be performed via telephone and the investigator will enter ultrasound results from the report provided.

